5.4.3.1 Resting 12-lead ECG

Twelve-lead ECGs will be obtained after the patient has been resting semi-supine for at least 10 minutes. All ECGs should be recorded with the patient in the same physical position. A standardised ECG machine should be used and the patient should be examined using the same machine throughout the study, where feasible. For Arm B8, central digital ECGs will be used.

For each time point, 3 ECG recordings should be taken within a 5 minute interval, but a window of up to -30 minutes is acceptable (as all the ECGs are triplicate). The mean QTcF interval from all 3 ECGs at any given time point should be considered for evaluation of eligibility and toxicity.

After paper ECGs have been recorded, the Investigator or designated physician will review each of the ECGs and may refer to a local cardiologist if appropriate. A paper copy should be filed in the patient's medical records. If an abnormal ECG finding at screening or baseline is considered to be clinically significant by the Investigator, it should be reported as a concurrent condition. For all ECGs, details of rhythm, PR, R-R, QRS, and QTc intervals and an overall evaluation will be recorded.

5.4.4 Vital signs

Vital signs including resting pulse, supine blood pressure (BP), respiratory rate, and body temperature measured in degrees Celsius, should be assessed at screening; before dosing on Day -7 of the lead-in; before dosing on Days 1, 8, 15, and 22 of each cycle; and at the EOT visit. Measurements should be taken in a supine position following at least 10 minutes of rest.

Vital signs for patients on AZD5069 will not be required for Day 8 and Day 22 visits beyond Cycle 2 as there are no dosing visits scheduled for patients on these days. Vital signs for patients in Arm B8 will not be required for Day 8 and Day 22 (all cycles) as there are no dosing visits scheduled for these patients on these days.

Height (in centimetres) will be obtained at screening.

Weight (in kilograms) will be obtained at screening, before dosing on Day -7 of the lead-in, before dosing on Day 1 of each cycle, and at the EOT visit. Weight obtained on Day -7 of the lead-in will be used to calculate the weight-related doses of AZD9150 (with the exception of Arm B8) for the lead-in. Weight obtained on Day 1 of each cycle will be used to calculate the weight-related dose of AZD9150 for each cycle. In Arm B8, a flat dose for AZD9150 and MEDI4736 will be administered. MEDI4736 will be administered as 1.5g flat dose Q4W. If body weight decreases to less than 30 kg, weight-based dosing (20 mg/kg Q4W) will be implemented from that cycle onwards.

The Investigator should assess any abnormal changes (i.e., changes that are out of range) in vital sign measurements for their clinical significance and determine if they require to be recorded as an AE.

5.4.5 Eastern Cooperative Oncology Group performance status (Other safety assessments)

Eastern Cooperative Oncology Group PS will be assessed at screening, before dosing on Day -7 of the lead-in, before dosing on Day 1 of each cycle, and at the EOT visit. The ECOG PS will be used to assess how a patient's disease is progressing, assess how the disease affects the patient's daily activities, and help the Investigator determine the appropriate treatment and progress. The ECOG scales and criteria are defined as follows:

- 0 = Fully active, able to carry out all predisease activities without restrictions
- 1 = Restricted in physically strenuous activity but ambulatory and able to carry out work of a light or sedentary nature (e.g., light housework, office work)
- 2 = Ambulatory and capable of self-care but unable to carry out any work activities. Up and about more than 50% of waking hours

3 = Capable of only limited self-care confined to bed or chair more than 50% of waking hours

4 = Completely disabled; cannot carry on self-care; totally confined to bed or chair

5 = Death

5.5 Pharmacokinetics

5.5.1 Collection of samples

Venous blood samples for analysis of AZD9150, AZD5069 and its metabolite AZ13587715, tremelimumab, and MEDI4736 will be obtained to determine the plasma concentrations of each of the various agents under investigation (see [Table 6](#) for the dose-escalation Part A and [Table 7](#) for the dose-expansion Part B of the study). The date and time of collection of each sample will be recorded. A window of 10% of the nominal time point is acceptable (e.g., ± 3 minutes for a 30-minute timepoint, ± 6 minutes for a 60-minute time point, etc.).

- For patients treated with **AZD9150** in Part A, PK blood samples for AZD9150 (Arms A1, A4 and A6) (2 mL) will be collected relative to the AZD9150 infusion as follows:
 - Lead-in, Day -7: Predose and at 0.5 hour (± 3 min), 1 (end of infusion; ± 6 min), 2 hours (± 12 min), 4 hours (± 24 min), and 6 hours (± 36 min) after the start of the infusion
 - Lead-in, Day -5: At 48 (± 4) hours after the start of the first infusion (on Day -7) and before the second infusion (on Day -5)
 - Cycle 1, Day 1: Predose
 - Cycle 2, Day 1: Predose and at 0.5 hour (± 3 min), 1 (end of infusion; ± 6 min), 2 hours (± 12 min), 4 hours (± 24 min), and 6 hours (± 36 min) after the start of the infusion
 - Cycle 3 and all subsequent odd-numbered cycles, Day 1: Predose
 - In Part B, only the first 10 patients randomised to treatment with AZD9150 alone or in combination with MEDI4736 (i.e., treatment arm B1, B3 or B5), will follow the schedule as in Part A. In patients following the first 10 patients randomised to treatment with AZD9150 alone or in combination with MEDI4736 (i.e., treatment arm B1 or B3) and in Arms B7 and B8, a predose and a 2 hour (± 12 min) sample will be collected on Day 1 of Cycle 2 and subsequent odd-numbered cycles.

- For patients treated with **AZD5069** (Arms A2 and A3) in Part A (**PRIOR TO DETERMINATION OF RP2D**), PK blood samples for AZD5069 and its metabolite AZ13587715 (2 mL total) will be collected as follows:
 - Lead-in, Day -7: Before the first morning dose and at 0.5 hour (± 3 min), 1 hour (± 6 min), 2 hours (± 12 min), 4 hours (± 24 min), 6 hours (± 36 min), 8 hours (± 48 min), and 10 hours (± 60 min) (when possible, if optional consent is provided) after the first morning dose
 - Cycle 1, Day 1: Before the morning dose and at 2 hours (± 12 min) after the morning dose
 - Cycle 2, Day 1: Before the morning dose and at 0.5 hour (± 3 min), 1 hour (± 6 min), 2 hours (± 12 min), 4 hours (± 24 min), 6 hours (± 36 min), 8 hours (± 48 min), and 10 hours (± 60 min) (when possible, if optional consent is provided) after the morning dose
 - Cycle 3 and all subsequent odd-numbered cycles, Day 1: Before the morning dose and at 2 hours (± 12 min) after the morning dose
 - Failure to obtain the 10 hour (± 60 min) samples will not be considered a protocol deviation

The morning dose of AZD5069 on Day -7 of the lead-in period and on any subsequent day where blood samples before the morning dose are required must be administered at the study centre and the precise time noted.
- In Part B, only the first 10 patients randomised to treatment **AZD5069** in combination with MEDI4736 (i.e., treatment arm B2 or B4), will follow the schedule as in Part A. In patients following the first 10 patients randomised to treatment with AZD5069 in combination with MEDI4736 (i.e., treatment arm B2 or B4), a predose and a 2 hour (± 12 min) sample will be collected on Day 1 of Cycle 2, and subsequent odd-numbered cycles.
 - Failure to obtain the 10-hour samples will not be considered a protocol deviation
 - The morning dose of AZD5069 on any day where blood samples before the morning dose are required must be administered at the study centre and the precise time noted.
- For patients treated with **AZD5069** monotherapy in Part B (i.e., treatment arm B6) PK blood samples for **AZD5069** and its metabolite AZ13587715 (2 mL total) will be collected as follows:
 - Cycle 2, Day 1: Before the morning dose

- Cycle 3 and all subsequent odd-numbered cycles, Day 1: Before the morning dose
- The morning dose of AZD5069 on any day where blood samples before the morning dose are required must be administered at the study centre and the precise time noted.
- For all patients in Part A and for patients randomised to receive **MEDI4736** in Part B (i.e., treatment arm B1, B2, B3, B4, or B7), PK blood samples for **MEDI4736** (3.5 mL) will be collected relative to the MEDI4736 infusion as follows:
 - Cycle 1, Day 1: Predose and 1 hour (± 6 min) after the start of the infusion (end of infusion)
 - Cycle 2, Day 15: Any time
 - Cycle 4 and all subsequent even-numbered cycles, Day 1: Predose
 - Cycle 8, Day 1: In addition to the predose sample, a sample at 1 hour (± 6 min) after the start of the infusion (end of infusion)
 - Follow-up: For patients who discontinue MEDI4736, a sample will be drawn 90 days after their last dose of MEDI4736 (coinciding with an IM [antidrug antibody (ADA)] sample)
- For all patients in treatment arm A4 in Part A, PK blood samples for tremelimumab (3.5 mL) will be collected relative to the tremelimumab infusion as follows:
 - Cycle 1, Day 1: Predose and 1 hour (± 6 min) after the start of the infusion (end of infusion)
 - Cycle 2, Day 15: Any time
 - Cycle 4, Day 1: Predose

Of the patients randomly assigned to treatment with AZD9150 alone in the dose-expansion Part B (treatment arm B5) and the first 12 patients for arm B7 will be asked to provide urine samples for AZD9150 PK assessments in urine (see [Table 7](#)). For Arm B8, up to 12 patients enrolled will be required to provide consent for urine samples for PK assessments (mandatory, USA only). For the subsequent patients enrolled in this arm, consent will be optional (see [Table 8](#)). Patients' consent to this evaluation will be documented on a separate ICF for urine sample collection. The date and time of collection and the weight of each urine collection will be recorded.

- For patients randomised to **AZD9150** alone (treatment arm B5) and first 12 patients for the Arm B7 who optionally consented to urine PK sampling and up to 12 patients of Arm B8 (mandatory, USA only)(or if optional consent was provided), urine PK samples (20 to 40 mL) will be collected from the total urine samples provided during each of the following collection intervals:
 - Lead-in, Day -7: 0 to 1, 1 to 6, and 6 to 24 hours after start time of AZD9150 infusion
 - Lead-in, Day -6 to -5: 24 to 48 hours after the start time of the first AZD9150 infusion
 - Cycle 1, Day 1: 0 to 1, 1 to 6, and 6 to 24 hours after start time of AZD9150 infusion. Note: The Cycle 1, Day 1, 6 to 24 hour time point is not required for treatment arm B8.

Note: Instructions will be provided to patients to collect these samples, as applicable, at home.

- For patients enrolled in treatment arm B8 to receive **AZD9150** 400 mg Q2W (200 mg in lead-in period) in combination with **MEDI4736** 1.5 g, PK blood samples for AZD9150 will be collected relative to the **AZD9150** infusion as follows:
 - Predose, 1 hour and 2 hours (± 12 min) on: Lead-in Day -7, and Day 1 of Cycle 1, Cycle 2, Cycle 3, Cycle 5, Cycle 7, Cycle 9, and Cycle 11 and then every 6 cycles
- For patients enrolled in treatment arm B8 to receive **AZD9150** 400 mg Q2W (200 mg in lead-in period) in combination with **MEDI4736** 1.5 g, PK blood samples for **MEDI4736** (3.5 mL) will be collected relative to the **MEDI4736** infusion as follows:
 - Cycle 1, Day 1: Predose and 1 hour (± 6 min) after the start of the infusion (end of infusion)
 - Cycle 2, Day 15: Predose
 - Cycle 4 and all subsequent even-numbered cycles, Day 1: Predose
 - Cycle 8, Day 1: In addition to the predose sample, a sample at 1 hour (± 6 min) after the start of the infusion (end of infusion)
 - Follow-up: For patients who discontinue **MEDI4736**, a sample will be drawn 90 days after their last dose of **MEDI4736** (coinciding with an IM [ADA] sample or prior to the initiation of a subsequent anticancer therapy).

The timing of the PK samples may be adjusted during the study, dependent on emerging data, in order to ensure appropriate characterisation of the plasma concentration-time profiles. The

total number of samples and the total volume of blood taken from each patient will not exceed those presented in Table 10, Section 5.8.3.

If a patient misses any doses of AZD9150 or AZD5069 within 3 days of PK sampling, please contact the AstraZeneca PK representative via the Medical Monitor [REDACTED] (see Section 6.10 for contact information) to inquire if changes in the timing of the PK assessments are required. (Note: All other assessments, including laboratory safety assessments, vital signs, and RECIST should continue to be performed as per study plan, relative to baseline assessments.)

Samples will be collected, labelled, stored, and shipped as detailed in the Laboratory Manual.

Any residual sample remaining after PK analysis has been performed may be used for exploratory biomarker research and characterisation of metabolites, if consent for this exploratory research has been obtained.

5.5.2 Determination of drug concentration

Samples for determination of AZD9150, AZD5069 and its metabolite AZ13587715, tremelimumab, and MEDI4736 will be analysed, using appropriate bioanalytical methods. Full details of the analytical method used will be described in a separate bioanalytical report.

All samples still within the known stability of the analytes of interest at the time of receipt by the bioanalytical laboratory will be analysed by a central laboratory on behalf of AstraZeneca.

Pharmacokinetic samples will be disposed of after the Bioanalytical Report finalisation or 6 months after issuance of the draft Bioanalytical Report (whichever is earlier), unless requested for future analyses.

5.5.3 Storage and destruction of pharmacokinetic samples

Pharmacokinetic samples will be disposed of after the Bioanalytical Report finalization or six months after issuance of the draft Bioanalytical Report (whichever is earlier), unless requested for future analyses.

Pharmacokinetic samples may be disposed of or destroyed and anonymised by pooling. Additional analyses may be conducted on the anonymised, pooled pharmacokinetic samples to further evaluate and validate the analytical method. Any results from such analyses may be reported separately from the Clinical Study Report (CSR).

Incurred sample reproducibility analysis, if any, will be performed alongside the bioanalysis of the test samples. The results from the evaluation will not be reported in the CSR but separately in a Bioanalytical Report.

Any residual back-up PK samples may be used for future exploratory biomarker research (in this case, residual back-up PK samples will be shipped to AstraZeneca biobank; see details in the Laboratory Manual).

5.6 Pharmacodynamics and patient selection biomarkers

Any sample collections listed in this Section may be discontinued at any time during the study at the Sponsor's discretion. See [Table 6](#) for the dose-escalation Part A and [Table 7](#) for the dose-expansion Part B of the study.

5.6.1 Collection of blood samples for pharmacodynamics assessments

In both the dose-escalation and safety cohorts Part A and dose-expansion Part B of the study, blood samples (2.5 mL) for evaluation of STAT3 RNA knockdown (secondary objective) and associated gene expression changes (exploratory objective)/pharmacodynamic RNA (AZD9150) will be collected from patients at screening; on Day -7 of the lead-in period; on Day 1 and Day 8 of Cycle 1; on Day 1 of all subsequent cycles; and at the EOT visit. The revised sample collection for pharmacodynamic RNA samples is applicable to newly enrolled patients only under protocol amendment 5, dated 10 May 2017 and onwards, existing patients will have samples collected up to Cycle 5, Day 1. New patients will be required to have samples collected beyond Cycle 5.

In both the dose-escalation (except safety cohorts A3, A4, and A6) Part A and dose-expansion Part B (B1-B6) of the study, blood samples (3.5 mL) for evaluation of circulating sPD-L1 protein (MEDI4736) will be collected from patients on Day 1 of Cycle 1; on Day 15 of Cycle 2; and on Day 1 of all subsequent even-numbered cycles. On Day 1 of Cycle 1 and on Day 1 of Cycle 8, in addition to the predose sample, a sample will also be obtained at the end of the MEDI4736 infusion. For patients who discontinue MEDI4736, a sample will be drawn 90 days after their last dose of MEDI4736 coinciding with an IM (ADA) sample. For patients in Arm B1, B2, and B4 sPD-L1 samples will not be collected after the first 20 patients. The sPD-L1 samples will also not be collected for Arms B7 and B8.

Details of pharmacodynamic blood sample collection, processing, shipping, and storage will be described in the Laboratory Manual.

5.6.2 Collection of blood for myeloid-derived suppressor cells

In both the dose-escalation Part A and dose-expansion Part B of the study, blood sample (5 mL for MDSC) will be collected: At screening, Day -7 of the lead-in period, Day 1 of Cycles 1, 2, 3, 5, and at the EOT visit. Samples will be used for quantification of MDSCs by flow cytometry using a multicolour panel of cell surface markers. Myeloid-derived suppressor cell levels at baseline and/or effect of treatment on MDSCs may predict clinical responses. For patients in Arm B1, B2, and B4 MDSC samples will not be collected after the first 20 patients. MDSC samples will also not be collected for Arms B7 and B8.

Details of sample collection, processing, shipping, and storage will be described in the Laboratory Manual.

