To assess tumor cell pharmacodynamics (STAT3 knockdown)	Pharmacodynamics of AZD9150 (STAT3 knockdown) in tumor tissue
To assess baseline circulating MDSCs and effect of treatment on circulating MDSCs (will not be evaluated for Arms B1, B2, and B4 post the first 20 patients and for Arms B7 and B8)	Circulating MDSCs
To evaluate baseline tumor PD-L1 expression for potential correlation with drug activity or the ability to prospectively identify patients likely to respond to treatment	Tumor PD-L1 expression

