- Follow-up: For patients who discontinue MEDI4736, a sample will be drawn 90 days after their last dose of MEDI4736 (coinciding with an IM [ADA] sample)
- ^d For all patients, 2 blood samples (2.5 mL each) for pharmacodynamic RNA (PDRNA) will be collected predose at each specified time point to assess pharmacodynamic response in blood for AZD9150 (STAT3 knockdown) and exploratory blood-borne biomarkers that may correlate to treatment or response (gene expression changes or modification of genomic DNA): At screening; on Day -7 of the lead-in period; on Day 1 and Day 8 of Cycle 1; on Day 1 of subsequent; and at the EOT visit. The revised sample collection for PDRNA samples is applicable to newly enrolled patients only (under protocol amendment 5, dated 10 May 2017, and onwards), existing patients will have samples collected up to Cycle 5, Day 1. New patients will be required to have samples collected beyond Cycle 5.
- ^e For all patients (except for patients in Arms A3, A4, and A6), a single blood sample (3.5 mL) will be collected predose at each specified time point to assess the pharmacodynamic response in blood for MEDI4736 (sPD-L1): Day 1 of Cycle 1, Day 15 of Cycle 2, and Day 1 of all subsequent even-numbered cycles. On Day 1 of Cycle 1 and on Day 1 of Cycle 8, in addition to the predose sample, a sample will also be obtained at the end of the MEDI4736 infusion.
- For patients who discontinue MEDI4736, a sample will be drawn 90 days after their last dose of MEDI4736 coinciding with an IM (ADA) sample.
- ^f For all patients, blood samples for MDSC (5 mL), will be collected predose at the specified time points to assess the treatment effect on circulating MDSCs: At screening; on Day -7 of the lead-in period; on Day 1 of Cycles 1, 2, 3, 5; and at the EOT visit.
- ^g For all patients, blood samples for IM (5 mL) will be collected predose on Day 1 of Cycle 1, on Day 15 of Cycle 2, and on Day 1 of each subsequent even-numbered cycle. For patients who discontinue MEDI4736, a blood sample will also be collected during follow-up at 90 days after the last dose of MEDI4736.
- ^h For patients treated with AZD9150, blood samples for IM (2 mL) will be collected relative to AZD9150 infusion as follows: Cycle 1, Day 1: Predose; Cycle 2, Day 1: Predose; and Cycle 4 and all subsequent even-numbered cycles, Day 1: Predose.

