- g Note: Instructions will be provided to patients to collect these samples, as applicable, at home. For all patients, 2 blood samples (2.5 mL each) for PDRNA will be collected predose at each specified time point to assess pharmacodynamic response in blood for AZD9150 (STAT3 knockdown) and exploratory blood-borne biomarkers that may correlate to treatment or response (gene expression changes or modification of genomic DNA): At screening, Day -7 of the lead-in period, Day 1 and Day 8 of Cycle 1, Day 1 of subsequent Cycles and at the EOT visit. The revised sample collection for PDRNA samples is applicable to newly enrolled patients only under protocol amendment 5, dated 10 May 2017 and onwards; existing patients will have samples collected up to Cycle 5, Day 1. New patients will be required to have samples collected beyond Cycle 5.
- h In patients randomized to receive MEDI4736 (i.e., treatment arms B1, B2, B3 and B4), a single blood sample (3.5 mL) will be collected predose at each specified time point to assess the pharmacodynamic response in blood for MEDI4736 (sPD-L1): Day 1 of Cycle 1, Day 15 of Cycle 2, Day 1 of all subsequent even-numbered cycles.
- On Day 1 of Cycle 1 and on Day 1 of Cycle 8, in addition to the predose sample, a sample will also be obtained at the end of the MEDI4736 infusion.
- For patients who discontinue MEDI4736, a sample will be drawn 90 days after their last dose of MEDI4736 coinciding with an IM (ADA) sample. sPDL samples will NOT be collected for the following patients: patients in B1, B2 and B4 post first 20 patients and patients in Arm B7
- i For all patients, blood samples for MDSC (5 mL), will be collected predose at the specified time points to assess the treatment effect on circulating MDSCs: At screening, Day -7 of the lead-in period, Day 1 of Cycles 1, 2, 3, 5, and at the EOT visit. MDSC samples will NOT be collected for the following patients: patients in B1, B2 and B4 post first 20 patients and patients in Arm B7.
- j In patients randomized to receive MEDI4736 (i.e., treatment arms B1, B2, B3, B4, and B7), blood samples for IM (5 mL) will be collected predose on Day 1 of Cycle 1, on Day 15 of Cycle 2, and on Day 1 of each subsequent even-numbered cycle. For patients who discontinue MEDI4736, a blood sample will also be collected during follow-up at 90 days after the last dose of MEDI4736.

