- Number of observations

The following summary statistics will be presented for CL, CL/F, CL_{ss}/F, volume of distribution, $t_{1/2\lambda_z}$, R_{ac}, A_e, and % dose excreted:

- Arithmetic mean
- Standard deviation
- Minimum
- Maximum
- Number of observation

The following summary statistics will be presented for T_{max} and T_{max ss}:

- Median
- Minimum
- Maximum
- Number of observations

The PK data for AZD9150, MEDI4736, tremelimumab, and AZD5069 will also be displayed graphically as appropriate. Displays will include plasma concentration patient profiles (on the linear and log-scale) versus time and gmean concentration (\pm standard deviation) versus time, stratified by cohort and others as necessary.

Pharmacodynamics

Pharmacodynamic variables will be summarised using descriptive statistics (n, mean, standard deviation, median, minimum, maximum) by visit and cohort.

Summaries of change from baseline and percent change from baseline will also be presented for pharmacodynamic variables by visit and cohort.

Immunohistochemistry scores will be plotted as a function of dose combination.

Histograms for each of the pharmacodynamic variables will also be presented by visit and dose.

Pharmacokinetics/pharmacodynamics

Scatterplots of each pharmacodynamic variable as a function of plasma concentrations of MEDI4736, AZD5069, tremelimumab, or AZD9150 may be presented.

Population analysis of pharmacokinetic/pharmacodynamic variables

The plasma concentration data for AZD9150, MEDI4736, tremelimumab, and AZD5069 may be analysed using a population PK approach, which may include exploring the influence of covariates on PK, if the data allow. A population pharmacodynamic approach will be used to investigate the relationship between PK and selected primary, secondary, and/or exploratory endpoints, where deemed appropriate. Results may be reported separately from the CSR for the main study. The PK, pharmacodynamic, demographic, safety, and tumor response data collected in this study may also be combined with similar data from other studies and explored using population PK and/or PK-pharmacodynamic methods. The results of any such analyses will be reported separately from the CSR.

Exploratory biomarker research and pharmacogenetics

Results will be reported separately and will not be part of the CSR.

Tumor response

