### 3.2.2. Dose-expansion Part B

The secondary objectives of the dose-expansion phase are to:

- Evaluate the safety and tolerability of AZD9150 and AZD5069 both as monotherapy and in combination with MEDI4736
- Assess secondary measures of efficacy (disease control rate [DCR] at 12 weeks; duration of overall response [DOR]; progression-free survival [PFS]; overall survival [OS]; and proportion of patients alive at 12 months)
- Assess the PK of AZD9150 and AZD5069 both as monotherapy and in combination with MEDI4736
- Assess the urinary pharmacokinetics of AZD9150 alone or in combination with MEDI4736
- Determine the IM of MEDI4736 in combination with AZD9150 or AZD5069
- Determine the IM of AZD9150 alone or in combination with MEDI4736
- Assess pharmacodynamic response in blood for AZD9150 and MEDI4736 (soluble PD-L1 will not be evaluated for Arms B1, B2, and B4 post the first 20 patients and for Arms B7 and B8)
- Assess tumour cell pharmacodynamics (STAT3 knockdown)
- Assess baseline circulating myeloid-derived suppressor cell (MDSC) and effect of treatment on circulating MDSCs (will not be evaluated for Arms B1, B2, and B4 post the first 20 patients and for Arms B7 and B8)
- Evaluate baseline tumour PD-L1 expression for potential correlation with drug activity or the ability to prospectively identify patients likely to respond to treatment

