#### 4.4. PHARMACODYNAMIC ENDPOINTS

The pharmacodynamic endpoints for dose-escalation Part A include the following:

- For AZD9150: Signal transducer and activator of transcription 3 (STAT3) knockdown in blood
- For MEDI4736: Soluble programmed cell death-ligand 1 (sPD-L1)
- For AZD5069: Circulating myeloid-derived suppressor cells (MDSCs)

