#### 10.1.3. Circulating Myeloid-Derived Suppressor Cells (MDSCs)

For all patients, blood samples for MDSC (5 mL), will be collected pre-dose at the specified time points to assess the treatment effect on circulating MDSCs: At screening, Day -7 of the lead-in period, Day 1 of Cycles 1, 2, 3, 5, and at the EOT visit.

For patients in Arm B1, B2, and B4 MDSC samples will not be collected after the first 20 patients. MDSC samples will also not be collected for Arms B7 and B8. Summary tables will report descriptive statistics including median results for circulating MDSC levels and the change from baseline by visit for each AZD5069 treatment group. A line plot with

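### SAP Section 10.1.3 tabulates circulating MDSC level and change for AZD5069 groups only and omits percent change, although the Part B objective names no drug and the protocol promises these summaries for every cohort

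*Protocol*

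**What the plan says.** **Collection.** Protocol Section 5.6.2 covers both parts: "In both the dose-escalation Part A and dose-expansion Part B of the study, blood sample (5 mL for MDSC) will be collected". The schedule is screening, Day -7, Day 1 of Cycles 1, 2, 3 and 5, and end of treatment, so up to seven samples per patient. The notes to Tables 6 and 7 in protocol Section 5.2 say "For all patients, blood samples for MDSC (5 mL), will be collected predose at the specified time points". The Table 7 notes then add the exceptions: "MDSC samples will NOT be collected for the following patients: patients in B1, B2 and B4 post first 20 patients and patients in Arm B7". Section 5.6.2 also excludes B8.

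**Objective.** Protocol Section 2.2 lists, under Part B, "To assess baseline circulating MDSCs and effect of treatment on circulating MDSCs". SAP Section 3.2.2 repeats it: "Assess baseline circulating myeloid-derived suppressor cell (MDSC) and effect of treatment on circulating MDSCs". Neither version names a drug. Both carry the same exceptions: B1, B2 and B4 after the first 20 patients, and B7 and B8. Part A has no MDSC objective in either document.

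**Protocol analysis.** Section 8.6 has change and percent change from baseline calculated for every patient for pharmacodynamic variables. Section 8.10 adds: "Summaries of change from baseline and percent change from baseline will also be presented for pharmacodynamic variables by visit and cohort".

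**SAP analysis.** Section 4.4 attaches the endpoint to one drug: "For AZD5069: Circulating myeloid-derived suppressor cells (MDSCs". Section 10.1.3 repeats the all-patient collection, then limits the summary tables to MDSC levels and "the change from baseline by visit for each AZD5069 treatment group". It adds a line plot of median levels over study days, split by treatment group, and a listing of all MDSC data. SAP Section 13 records one change from the protocol, the important-deviation wording added to three analysis sets.

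**The concern.** A secondary objective that covers both drugs is given an analysis that tabulates one of them. The exceptions written into the objective show that this is not its intended scope. B1, B7 and B8 are AZD9150 arms, and there would be no reason to exclude them from an objective that applied to AZD5069 alone. B3 and B5 carry no exception, so they are in scope.

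If the table shells follow Section 10.1.3, the clinical study report will contain no tabulated MDSC level or change for AZD9150, although patients in those arms gave the same samples. Percent change, which the protocol promises, will be missing for every arm. Because Section 13 is silent, a reader of the report could not tell that the omission was a choice.

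**Working it through.** The documents state no sample size, power or precision figure for MDSCs, so there is nothing to reproduce. The check sets sampled arms against tabulated arms and then counts patients.

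**Step 1. Arms.** A5 and A7 never opened, and B7 and B8 are not sampled.

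| | AZD9150 | AZD5069 |
|---|---|---|
| Part A, sampled | A1, A4, A6 | A2, A3 |
| Part B, sampled | B1, B3, B5 | B2, B4, B6 |
| Table of level and change in SAP 10.1.3 | none | all five |
| Table of percent change | none | none |
| Listing | all | all |
| Median-level plot | unclear | yes |

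Sampled arms: 6 + 5 = 11. Tabulated: 5 of 11. This count needs no assumption about patient numbers.

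**Step 2. Part B patients.** Planned sizes are in protocol Section 8.2.2: 10 to 52 in each of B1 and B2, 12 to 35 in each of B3 and B4, and 12 in each of B5 and B6. Assumption: the cap at the first 20 applies separately to B1, B2 and B4. The documents do not say so explicitly.

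- Planned maxima: AZD9150 = 20 (B1) + 35 (B3) + 12 (B5) = 67. AZD5069 = 20 (B2) + 20 (B4) + 12 (B6) = 52. Share outside the tables = 67 / (67 + 52) = 67/119 = 56%.
- Planned minima: AZD9150 = 10 + 12 + 12 = 34. AZD5069 = 10 + 12 + 12 = 34. Share = 34/68 = 50%.

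These are planned, not actual, numbers. The protocol synopsis says that first-line patients enrolled in B3 were replaced, so 35 is not a hard ceiling for sampled B3 patients.

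**Step 3. Does other SAP text fill the gap?** Section 6.1 says that pharmacodynamic variables are summarised with the usual continuous statistics. Section 6.1.1 puts two combination groups, which between them contain all B3 patients, into every summary. Both pull against Section 10.1.3, but that section is the specific instruction for MDSC tables and is the one a programmer would follow. Neither general section supplies percent change.

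**Step 4. Are the missing tables deferred to another report?** The SAP says so where it intends it: Section 10.1.1 for STAT3 knockdown and Section 10.1.4 for post-baseline tumour PD-L1. Section 10.1.3 says nothing of the kind.

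**The case against.** The strongest defence is that the restriction is deliberate. SAP Section 4.4 assigns STAT3 to AZD9150, soluble PD-L1 to MEDI4736 and MDSCs to AZD5069. Protocol Section 1.1.2 gives a reason, since CXCR2 regulates the movement of MDSCs into tumours. Pharmacodynamic analyses are descriptive only, all values are listed, and no decision rule or primary result depends on MDSC tables. Protocol Section 5.6.4 also allows results to be reported outside the study report.

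That explains why AZD5069 comes first. It does not change the objective or protocol Sections 8.6 and 8.10, and a descriptive objective still needs its descriptive tables. The limited importance does stand.

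Three stronger readings are tempting, and the documents do not support them:

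- A reader might infer that an objective covering all arms goes unmet. The objective is Part B only and has its own exceptions. Leaving A1, A4 and A6 out of the tables conflicts with protocol Section 8.10 but leaves no Part A objective unmet.
- A reader might infer that AZD9150 data are not summarised at all. The plot is split by treatment group with no stated drug limit, so AZD9150 medians may appear there. It shows level, not change, and its scope is uncertain because it follows directly on the AZD5069 sentence.
- A reader might infer that the AZD5069 results cannot be interpreted without the AZD9150 arms, in particular that the MEDI4736 effect cannot be separated. B6 is AZD5069 alone and is randomised alongside B4, so the planned tables already allow that contrast. Samples at Day -7 and before dosing on Cycle 1 Day 1 also precede any MEDI4736. The AZD9150 arms are active concurrent arms, not neutral controls, and the comparison is randomised only among patients eligible for AZD5069.

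**Conclusion.** The point holds as a mismatch between the SAP and the protocol that leaves a secondary objective partly unreported. SAP Section 10.1.3 gives B1, B3 and B5 no tabulated MDSC level or change from baseline, drops percent change everywhere, and departs from protocol Sections 8.6 and 8.10 without a declaration in SAP Section 13. A1, A4 and A6 are also untabulated, contrary to Section 8.10. The firm measure of size is 5 of 11 sampled arms. The 50% to 56% of Part B patients depends on planned sizes and on reading the first-20 cap per arm. The primary endpoint and the adaptive rules are unaffected. It should still be corrected, because a stated instruction delivers less than the objective requires and the data are already being collected.

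**What to change.** In SAP Section 10.1.3, replace the restriction to AZD5069 groups with *each treatment group with MDSC samples*, add percent change from baseline, and state that the median plot covers the same groups. Amend Section 4.4 so that MDSCs are not labelled as an AZD5069 endpoint alone. If the sponsor prefers to keep the restriction, Section 13 should declare and justify it, although the objective would then remain only partly reported.

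Showing B3 beside B4, B5 beside B6 and B1 beside B2 would be a helpful descriptive layout but is optional. If it is used, a footnote should say that the arms are randomised against each other only among patients eligible for AZD5069. Building separate tables for that subset is not needed to close the gap.

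The cost is extra columns and one more derived variable in tables already planned. No further samples or data are required.
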